## ABSTRACT

The ART study (Adjuvant Rituximab in TTP) is a pilot safety/efficacy study of adjuvant low dose rituximab (100 mg/week x 4 doses) plus standard plasma exchange and corticosteroids for the treatment of thrombotic thrombocytopenic purpura (TTP) with severe ADAMTS13 deficiency. Results for study subjects will be compared to historical controls treated initially with plasma exchange and corticosteroids. This study proposes to test the hypothesis that adjuvant low dose rituximab may decrease the incidence of composite primary endpoint (exacerbations or refractory disease) in acquired TTP with severe ADAMTS13 deficiency. A novel ADAMTS13 assay will be used to identify patients with TTP and severe ADAMTS13 deficiency for enrollment, and to assess the utility of ADAMTS13 as a biomarker for response to therapy and prognosis.

## DEFINITIONS

**Day 1:** The first day a subject receives plasma exchange for treatment of TTP.

**Treatment Response:** 2 consecutive days with platelet count  $\geq 150,000/\mu\text{L}$

**Durable Treatment Response:** Treatment Response that persists for  $\geq 30$  days after discontinuation of plasma exchange.

**Exacerbation:** Recurring TTP  $\leq 30$  days after a Treatment Response and discontinuation of plasma exchange.

[figure not shown]
**Refractory TTP:** Failure to achieve a Treatment Response by day 28, or failure to achieve a Durable Treatment Response by day 60.

**Composite Primary Endpoint:** Exacerbation or Refractory TTP.

**Relapse:** Recurring TTP  $> 30$  days after Treatment Response.

**Observation Period:** The interval of 2 years after a subject first achieves a Durable Treatment Response.

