### 5.2.3 Treatment of Exacerbation with Plasma Exchange and Corticosteroids.

If a subject achieves a Treatment Response by day 28 and subsequently has a platelet count (confirmed by a repeat count)  $\leq 120,000/\mu\text{L}$  within 30 days after stopping plasma exchange, then plasma exchange and corticosteroid treatments are to be restarted as described under **section 5.2.1**. The confirmatory platelet count must be a discrete collection drawn 1 to 24 hours after the first collection.

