### 5.2.4 Stopping Treatment of Exacerbation with Plasma Exchange and Corticosteroids

After an early exacerbation plasma exchange is to be stopped and corticosteroids tapered when the subject has a platelet count  $\geq 150,000/\mu\text{L}$  on 3 consecutive days.

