### 5.2.5 Treatment of Refractory TTP

The subject will be considered to have Refractory TTP if they do not have a Treatment Response by day 28, or do not have a Durable Treatment Response by day 60. The treatment of Refractory TTP will include resuming plasma exchange and corticosteroids. Additional salvage therapy is at the physician's discretion and can include full dose rituximab  $375 \text{ mg/m}^2$  weekly for 4 doses. Patient with Refractory TTP will be followed for 2 years with laboratory monitoring.

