#### **6.1.5 After Plasma Exchange is stopped (Table 4)**

- 1) First month
  - Surveillance panel – one per week  $\pm$  2 days
  - Chemistry panel – one per week  $\pm$  2 days
  - ADAMTS13 activity and antibody – on day 7  $\pm$  2 days and day 30  $\pm$  7 days after plasma exchange is stopped
  - Peripheral smear – on day 7  $\pm$  2 days after plasma exchange is stopped
  - Clinical status (Follow-Up Post-PE CRF) and Concomitant Medication Log – one per week  $\pm$  2 days
- 2) Months 1 to 3
  - Surveillance panel – one per month  $\pm$  7 days
  - Chemistry panel – one per month  $\pm$  7 days
  - ADAMTS 13 activity and antibody – one at 3 months  $\pm$  7 days after plasma exchange is stopped
  - Clinical status (Follow-Up Post-PE CRF) and Concomitant Medication Log – one per month  $\pm$  7 days
- 3) Months 4 to 24
  - Surveillance panel – every 3 months for one year after plasma exchange is stopped  $\pm$  14 days
  - Chemistry Panel – one year after plasma exchange is stopped  $\pm$  14 days
  - ADAMTS13 activity and antibody – every 3 months  $\pm$  14 days
  - Clinical status (Follow-Up Post-PE CRF) and Concomitant Medication Log – every 3 months  $\pm$  14 days

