#### **6.1.7 Refractory TTP (Table 5)**

- 1) ADAMTS13 activity and antibody – during the first day after Refractory TTP is diagnosed and then at least every 3 months for 2 years thereafter  $\pm$  14 days
- 2) Serum IgG, IgM, IgA – 1 year after Refractory TTP is diagnosed  $\pm$  14 days
- 3) Clinical status and medication log – every 3 months for 2 years  $\pm$  14 days
- 4) If patient receives standard dose of rituximab as a salvage therapy, the B lymphocyte and rituximab level will be measured based on schedules described in section 6.1.9 and table 6.

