**Table 4: Schedule of Measurements After Plasma Exchange (PE) is Stopped for Treatment Response**

	First 30 days of no PE	Months 1 to 3	4 Months to 2 years
Assessment			
Clinical status	1 per week $\pm$ 2 days	1 per month $\pm$ 7 days	Every 3 months for 2 years $\pm$ 14 days
Medication log	1 per week $\pm$ 2 days	1 per month $\pm$ 7 days	Every 3 months for 2 years $\pm$ 14 days
Laboratory			
Surveillance Panel	1 per week $\pm$ 2 days	1 per month $\pm$ 7 days	Every 3 months for 1 year after first PE $\pm$ 14 days
Chemistry Panel	1 per week $\pm$ 2 days	1 per month $\pm$ 7 days	1 year after first PE $\pm$ 14 days
ADAMTS13 activity and antibody	Day 7 $\pm$ 2 days and day 30 $\pm$ 7 days	1 at month 3 $\pm$ 14 days	Every 3 months for 2 years after first PE $\pm$ 14 days
Peripheral smear	Day 7 $\pm$ 2 days		
Serum IgG, IgM and IgA			One year after first PE $\pm$ 14 days

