**Table 5: Schedule of Measurements When Refractory TTP is diagnosed**

Assessment	Frequency
Clinical status	4 times per year (quarterly) after the first PE for 2 years $\pm$ 14 days
Medication log	After the first PE for 2 years $\pm$ 14 days
Laboratory	
Serum IgG, IgM, IgA	1 year after the first PE $\pm$ 14 days
ADAMTS13 activity and antibody	On the day Refractory TTP is diagnosed Then every 3 months up for 2 years $\pm$ 14 days

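### Section 5.2.5 tells sites to resume plasma exchange and steroids in a re-treated exacerbator who is in response on day 60, if the last exchange fell on days 31 to 59

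*Combined protocol and SAP*

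**What the plan says.** The day count starts at the first plasma exchange. The Definitions ask for at least 30 days of sustained response once exchange has ended before a response is durable, and they define Refractory TTP as "Failure to achieve a Treatment Response by day 28, or failure to achieve a Durable Treatment Response by day 60". Section 5.2.5 repeats that rule and continues: "The treatment of Refractory TTP will include resuming plasma exchange and corticosteroids". It adds discretionary salvage, including full-dose rituximab, and two years of laboratory follow-up. It sets no condition on the platelet count or on active TTP.

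Exacerbations have their own pathway. Section 5.2.3 covers a confirmed fall to 120,000/µL or below "within 30 days after stopping plasma exchange, then plasma exchange and corticosteroid treatments are to be restarted". Section 5.2.4 then gives the stopping rule, triggered by three daily counts in a row at or above 150,000/µL: "After an early exacerbation plasma exchange is to be stopped and corticosteroids tapered".

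Two visit schedules could apply afterwards. Table 4 is the "Schedule of Measurements After Plasma Exchange (PE) is Stopped for Treatment Response", and section 6.1.5 gives, for the first month, "Surveillance panel – one per week" (that panel is the CBC and LDH). For Refractory patients, section 6.1.7 asks for ADAMTS13 testing "during the first day after Refractory TTP is diagnosed and then at least every 3 months for 2 years thereafter", and Table 5 likewise has "On the day Refractory TTP is diagnosed Then every 3 months up for 2 years". Both also list immunoglobulins, clinical status and a medication log. Neither lists the surveillance panel.

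**The concern.** The day-60 limb of the Refractory definition measures time off exchange as well as disease. A patient can be well on day 60 and still fail it because re-treatment for an exacerbation ended too recently. Section 5.2.5 then treats that patient like someone with active disease: one section has exchange stopped and steroids tapered, and the next has both resumed.

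At stake is needless exposure to exchange and steroids, and a possible opening to salvage rituximab, in a patient in remission. Section 2.1 itself cites a study reporting a 31% risk of major complications with exchange, including 3% fatality. That shows why the instruction matters, but it is not the risk of one resumption.

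The second issue is follow-up. If a site sensibly ignores the instruction but takes the Refractory label to mean Table 5, no platelet count is scheduled for the rest of the 30-day window in which section 5.2.3 acts on the platelet count. The two problems are alternatives: if exchange is resumed, section 6.1.4 and Table 3 bring a daily surveillance panel.

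**Working it through.** The plan gives no figure on this point. Its sample-size figure in section 9.1 (14 treated against 40 controls, 10% against 55%) reproduces at 90.7% power with a pooled normal approximation, two-sided 5%, no continuity correction. Nothing below touches it.

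**1. Cut-off.** Let L be the day of the last exchange. A durable response is reached on day L + 30 at the earliest. Reaching it by day 60 requires L ≤ 60 − 30 = 30. A patient off exchange and in response on day 60 is therefore Refractory if L is 31 to 59, and not if L ≤ 30.

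**2. A compliant path that is caught.** Response and end of exchange on day 10; exacerbation on day 25, which is 15 days later and so inside the 5.2.3 window; last re-treatment exchange on day 35 under 5.2.4. On day 60 the patient is 60 − 35 = 25 days off exchange and in response. Durable response would come on day 35 + 30 = 65, so the patient is Refractory on day 60. A single exchange resumed that day would move the earliest durable response to day 60 + 30 = 90.

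**3. Paths that are not caught.** Response day 6, exacerbation day 12, last exchange day 19: durable response on day 49, not Refractory. Last exchange on day 30: durable response on day 60, not Refractory. A patient who responds as late as day 28, stops exchange then and never exacerbates reaches day 58. So where response is otherwise maintained and exchange stops at response, the day-60 limb catches re-treated exacerbators.

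**4. How wide the gap is on the calendar.** Assume the fastest re-treatment, with the last exchange two days after the exacerbation (L = e + 2). For first response and end of exchange on day r, the exacerbation day e can be r + 1 to r + 30, and 31 ≤ L ≤ 59 means e from 29 to 57.

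| First response (day) | Possible e | Caught | Days caught of 30 |
|---|---|---|---|
| 10 | 11–40 | 29–40 | 12 |
| 14 | 15–44 | 29–44 | 16 |
| 20 | 21–50 | 29–50 | 22 |
| 28 | 29–58 | 29–57 | 29 |

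In the last row, e = 58 gives L = 60, so the patient is still on exchange on day 60. These are calendar days, not patient probabilities; the documents give no exacerbation timing.

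**5. Platelet counts at stake.** The 30-day window ends on day L + 30, so L − 30 days of it remain after day 60. Take the weekly Table 4 counts as days 7, 14, 21 and 28 off exchange.

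| Last exchange (day) | Window left after day 60 (days) | Weekly counts after day 60 |
|---|---|---|
| 31 | 1 | 0 |
| 35 | 5 | 1 |
| 42 | 12 | 2 |
| 52 | 22 | 3 |
| 59 | 29 | 4 |

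**6. Primary endpoint.** The composite is Exacerbation or Refractory TTP. Every patient in steps 2 and 4 has already had an exacerbation, so the Refractory label adds nothing to the count.

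**7. Patients.** With 20 enrolled, the assumed 10% rate gives 20 × 0.10 = 2 expected composite events; at the historical 55% it would be 20 × 0.55 = 11. Late, re-treated exacerbators in response on day 60 are some unknown part of that.

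**The case against.** The best defence is that nobody would follow 5.2.5 literally. Nearly the same sentence appears in section 5.2.6, where it plainly concerns recurring disease. The word resuming also fits badly for a day-28 non-responder still on exchange. This looks like loose shared wording meant for active TTP, and 5.2.4 is the more specific rule for a re-treated exacerbator. That is a plausible account of the intent. It does not remove the conflict, because 5.2.5 applies by its terms to everyone without a durable response by day 60, and up to six sites (section 4.1) should not each have to decide to override it. The study schema and a figure in the Definitions are not shown in the text available; a clarification there would still leave these sections in conflict.

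Several stronger readings are tempting, and the documents do not support them:

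- *Every re-treated exacerbator becomes Refractory.* No; only those whose last exchange falls after day 30.
- *The primary result is distorted.* No composite status changes, and section 9.2 plans no separate analysis of Refractory TTP.
- *Platelet monitoring stops on day 60.* That follows only if Table 5 replaces Table 4, which the text does not say. Table 4's title describes this patient, and Table 5 can be read as additional.
- *The endpoint definition must be rewritten and the control charts rechecked.* A fixed day-60 horizon is a legitimate choice, and no reported case depends on changing it.
- *The Relapse wording needs repair too.* Relapse is counted from response and Exacerbation from response and end of exchange, but the overlap is 0 days if response and last exchange coincide, and 1 day if one more exchange follows.

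**Conclusion.** The point holds in a limited form. For a re-treated exacerbator with the last exchange on days 31 to 59 and ongoing response on day 60, the written protocol gives contradictory treatment instructions and does not say which schedule governs. The day-30 cut-off follows directly from the definitions. The calendar-day counts rest on the assumed fastest re-treatment, and the panel counts on weekly visits at their nominal days. The number of patients affected cannot be estimated without exacerbation timing, but it is likely to be small in a 20-patient study. The composite endpoint, the historical rate and the sample size are unaffected. Severity is minor: a wording correction, worth making because following the text as written would expose a patient in remission to treatment that the protocol has just ended.

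**What to change.** Make two changes, both outside the endpoint definitions.

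1. In section 5.2.5, make resumption of exchange and corticosteroids conditional on the patient not being in Treatment Response, that is, on active TTP or a confirmed low platelet count. The sponsor should name the threshold; the confirmed count of 120,000/µL or below in 5.2.3 is already in the protocol.
2. In 5.2.5 or 6.1.7, state that a patient who is off exchange and in response on day 60 stays on the Table 4 schedule until at least 30 days after the last exchange, with the 6.1.7 and Table 5 measurements added.

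Leave the day-60 Refractory definition, the 55% historical rate and the Relapse definition as they are. The cost is about two sentences in an amendment. At most four weekly panels per affected patient become explicit, and only where a site would otherwise have used Table 5 alone. No control charts need re-abstraction and no analysis changes.

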**Study Schemata:**

## 1. OBJECTIVES

This study will evaluate the effect of low dose adjuvant rituximab combined with plasma exchange and corticosteroids on the course of TTP and severe ADAMTS13 deficiency (<10% activity).

### 1.1 Primary Endpoint

- Incidence of composite primary endpoint, Exacerbation or Refractory TTP

### 1.2 Secondary Endpoints

#### 1.2.1 Clinical and Safety Endpoints

- Incidence of Durable Treatment Response
- Number of days to Durable Treatment Response
- Number of plasma exchanges to Durable Treatment Response
- Incidence of relapse
- Numbers of days to relapse
- 4 week, 1 year and 2 year incidence of death
- Incidence, type and severity of treatment-related adverse events

#### 1.2.2 Laboratory Objectives

- Assess the relationship of ADAMTS13 enzyme activity and ADAMTS13 autoantibody titer to indicators of disease activity including:
  - Primary and secondary clinical endpoints
  - Platelet count
  - LDH
  - B cell depletion and recovery
- Assess the relationship of rituximab levels to the extent and duration of B cell depletion
- Describe the effect of plasma exchange on rituximab levels

## 2. BACKGROUND AND SIGNIFICANCE

### 2.1. Utility of ADAMTS13 data in TTP

The introduction of plasmapheresis with plasma exchange has increased survival in patients with TTP from less than 10 percent to 80 percent and is the only therapy demonstrated to be effective in a randomized clinical trial (Rock 1991). Plasma exchange rapidly restores circulating levels of the von Willebrand factor cleaving protease, ADAMTS13, and removes inhibitors to the enzyme. Although clearly beneficial, plasma exchange does not correct the primary cause of the disorder. More than 30% of patients with TTP have at least one relapse within 2 years (Kremer 2008). In addition plasma exchange may itself cause significant morbidity. One study documents a 31% risk for major complications, including a 3% fatality rate (McMinn 2003).

An autoimmune etiology of acquired TTP in adults is strongly supported by the finding of circulating ADAMTS13 inhibitors due to IgG autoantibodies. These inhibitors are found in 48 to 80% of individuals with idiopathic TTP (Moake 2002, Tsai 2003, Veyradier 2001). ADAMTS13, a von Willebrand factor-cleaving protease, regulates the size of von Willebrand factor (VWF) multimers. Deficiency of ADAMTS13 activity is associated with persistence of ultra large molecular weight VWF (ULVWF) multimers. ULVWF avidly binds to platelets, leading to

microvascular platelet deposition, the hallmark of TTP. Subsequent series identified severe ADAMTS13 activity deficiency in 30% to 80% of cases of TTP (Lammle 2005).

Although severe deficiency of ADAMTS13 activity (<5%) appears to be specific for TTP, the syndrome can also be seen in subjects with less severe deficiency and even normal levels of ADAMTS13 making diagnostic decisions difficult (George 2004). However, the risk of relapse is higher (~45%) for patients with persistent severe ADAMTS13 deficiency during remission, and essentially all of these patients have severe ADAMTS13 deficiency when they relapse (Zheng 2004). ADAMTS 13 inhibitors also correlate with relapses, delayed response to plasma exchange, refractory disease, and early death (Zheng 2004, Bohm 2005, Coppo 2006, Kremer Hovinga 2010).

Based on these studies, measurement of ADAMTS13 activity and inhibitor level may be useful to identify patients with TTP who can benefit from immunosuppressive therapy in addition to plasma exchange. However, current ADAMTS13 assays have limited sensitivity, especially for detecting inhibitors. At BJH, ADAMTS13 assays have a turnaround time of 3 to 7 days, which is too slow to be useful for therapeutic decisions. To address these points, [name] laboratory has developed a new fluorogenic ADAMTS13 substrate that has substantially increased sensitivity for measuring ADAMTS 13 activity and inhibitor titer. Results can be available in <24 hours, increasing the practical use of this assay in patient management.

## 2.2 Efficacy of Rituximab in TTP

Refractory or relapsing TTP has been treated with a variety of immunosuppressive agents (Ziman 2005, Bell 1991, Alford 2003). The most consistently effective of them is rituximab, a chimeric monoclonal antibody directed at the CD20 antigen expressed on the surface of B lymphocytes. Rituximab has been used successfully in the therapy of B-cell malignancies (O'Brien 2001, Plosker 2003, Cartron 2004). Efficacy has also been demonstrated in autoimmune disorders. Stasi et al., observed a 52% response rate of immune thrombocytopenic purpura with rituximab (Stasi 2001) and an 80% response rate of acquired anti-factor VIII antibodies (Stasi 2004). Rituximab-mediated B cell depletion occurs by several mechanisms including complement mediated cell lysis and antibody-dependent cellular cytotoxicity (Cartron 2004). In animal experiments, peripheral blood B-cells are reduced to undetectable levels (>95% depletion) within 24 hours after infusion (Reff 1994) and lymphopenia persists for as long as 8 days. The majority of lymph node B-cells are depleted within 15 days after weekly antibody treatment, requiring 60 to 90 days to reach normal levels. Based on the recovery of peripheral blood B-cells approximately 8 days after single dosing, a weekly infusion schedule has been adopted in the treatment of B-cell malignancies.

The use of rituximab in the treatment of TTP has recently been reviewed. Of 73 evaluable patients with TTP due to immune-mediated ADAMTS13 deficiency, the majority (95%) achieved a complete remission within 2-3 weeks of the first dose of rituximab. Relapses were reported in 10 of 69 responding patients (14%), with a median time to relapse of 22 months. For patients not treated with rituximab, the expected relapse rate is as high as 60%. However, the favorable results with rituximab should be interpreted cautiously given the relatively short median duration of follow-up of approximately 10 months. Rituximab was generally well tolerated, with few serious adverse events reported. Three severe infectious complications were identified, including viral reactivation in keeping with black box warnings for this agent (Elliot 2009).

Experience with rituximab in TTP at Washington University was reviewed by Ling et al (2009). Twelve of 13 patients (92%) with severe ADAMTS13 deficiency (<10%) achieved a complete response; no relapses occurred with a median follow-up of 24 months (range, 13–84

months). Of eight patients with available ADAMTS13 data after rituximab treatment, seven had recovery of normal ADAMTS13 activity and disappearance of a detectable inhibitor (Ling 2009).

A prospective study in France (Froissart 2012) compared 22 adults with refractory TTP treated with rituximab and plasma exchange to 53 historical controls who received plasma exchange with or without vincristine. The time to a durable remission was significantly shorter for patients receiving rituximab ( $P = 0.03$ ), although the plasma volume required to achieve a durable remission was not significantly different compared to controls. Of the rituximab-treated patients, none relapsed within the first year although three relapsed up to 3 years later. Treatment with rituximab produced a rapid and profound depletion of peripheral B-cells that lasted 9 months and correlated with a higher level of ADAMTS13 activity and lower antibody titers. These differences were no longer significant after 12 months. No severe side effects occurred.

Thus, treatment with rituximab normalizes ADAMTS13 and induces durable remissions in >90% of patients with refractory or relapsing TTP. Late relapses have occurred in ~10% of these patients after 9 months to 4 years; all but one had a prolonged remission when retreated with rituximab (Sadler 2008). These results suggest that adjuvant rituximab might increase the rate of remission and reduce relapses for patients with severe ADAMTS13 deficiency at diagnosis. In fact, a recent study of adjuvant full dose rituximab (375 mg/m^2 weekly x 4) observed a 10% relapse rate compared to 57% in historical controls (Scully 2011).

